2.8 Withdrawal of Subjects

2.8.1 Criteria for Early Withdrawal

The following events are considered sufficient reason to discontinue a subject from the study:

- Subjects are free to withdraw from the study at any time, for any reason, and without prejudice.
- The subject is non-compliant.
- The subject experienced an AE that in the investigator's opinion precludes continued participation.
- The subject incurred a significant protocol violation that constitutes a safety hazard or significantly confounds the interpretation of the data from that subject.
- At the Sponsor's request.
- The study is terminated.

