DOCUMENT TYPE:	Clinical protocol		
DOCUMENT NUMBER:	100-501 NCT: NCT03763929		
COMPOUND:	Trans Sodium Crocetinate		
STUDY TITLE:	Double-Blind, Randomized, Placebo-Controlled, Phase 2 Study of Efficacy and Safety of Trans Sodium Crocetinate (TSC) Administered Onboard Emergency Vehicles for Treatment of Suspected Stroke: PHAST- TSC		
CLINICAL PHASE:	2		
INDICATION:	Treatment of suspected stroke victims in the emergency vehicle		
IND NUMBER:	138575		
SPONSOR:	Diffusion Pharmaceuticals Inc. [name]		
DOCUMENT VERSION/STATUS:	Final		
DOCUMENT RELEASE/AMENDMENT DATE:	Amendment 5: November 18, 2019 Amendment 4: November 19, 2018 Amendment 3: August 22, 2018 Amendment 2: August 2, 2018 Amendment 1: March 19, 2018 February 16, 2018		

Diffusion Pharmaceuticals Inc	Confidential	TSC injectable
Protocol 100-501: November 18, 2	019	Page 9 of 69

	SYNOPSIS		
Title	Double-Blind, Randomized, Placebo-Controlled, Phase 2 Study of Efficacy and Safety of Trans Sodium Crocetinate (TSC) Administered Onboard Emergency Vehicles for Treatment of Suspected Stroke: PHAST-TSC		
Protocol No.	100-501		
Study Phase	2		
Study Design	Double-blind, randomized, placebo-controlled, phase 2 preliminary efficacy and safety trial of Trans Sodium Crocetinate (TSC) as first-line treatment of suspected stroke subjects in the emergency vehicle.		
Study Population	Ambulance-transported subjects identified as having an acute stroke using the modified Los Angeles Prehospital Stroke Screen (mLAPSS) screen, who are within 2 h of last known well time.		
Number of Subjects	160 subjects that meet all protocol inclusion/exclusion criteria.		
Study Centers	Up to 30 stroke receiving hospitals.		
Objective	To assess the potential efficacy and safety of TSC as early treatment for both ischemic and hemorrhagic stroke when administered while subject is in ambulance being transported to hospital.		
Endpoints	 Primary Efficacy Endpoint: Global disability level on the utility-weighted modified Rankin Score (UW-mRS) Assessment at 90 days in all subjects Secondary Efficacy Endpoints: Functional independence (mRS 0-2) in all subjects Global disability level on the UW-mRS in ischemic stroke subjects Functional independence (mRS 0-2) in ischemic stroke subjects Exploratory Efficacy Endpoints: Freedom from disability (mRS 0-1) Barthel Index (BI) National Institutes of Health Stroke Scale (NIHSS) Stroke Impact Scale (SIS-16) AMC-Linear Disability Scale 		

SYNOPSIS

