2.2 Design Overview

This is a multicenter, randomized, placebo-controlled, double-blind, parallel group trial of intravenous trans sodium crocetinate (TSC) initiated by paramedics in the field within 2 hours of symptom onset in 160 subjects with acute stroke. The primary objectives of the study are to evaluate the efficacy and safety of field-initiated TSC in improving the long-term functional outcome of subjects with acute stroke. Subjects with acute stroke will be identified in the field by emergency medical service responders who have received training in basic and advanced cardiac life support, stroke recognition, and specific procedures relevant to the proposed study. Paramedics will deliver the single, field, bolus dose of study agent, TSC at 0.25 mg/kg or matched placebo, followed after hospital arrival by standard of care (SOC). No additional study drug will be administered in the hospital. Follow-up assessments will be performed at Emergency Department (ED) arrival, 24 hours, 48 hours, Day 4, Day 30, and Day 90. The study will be performed at up to 30 receiving hospital sites.

Across all preclinical models and in human acute ischemic stroke, the relation between time from onset and response to beneficial therapy in acute ischemic stroke is a graded one of continuous decline with time, rather than square-shaped, characterized by uniform high benefit until a sudden drop to no benefit at a particular time point. Across all neuroprotective and reperfusion treatments in preclinical models, and for both the proven human reperfusion therapies (IV fibrinolysis and endovascular mechanical thrombectomy), treatment is most efficacious if started at 30 mins rather than 60 mins, at 1h rather than 2h, at 2h rather than 3h, and at 3h rather than 4h.

A consequence of this graded relationship is that the sample sizes required to detect beneficial effect of a treatment agent are moderate for subjects treated sooner after onset, when the magnitude of benefit is largest. But the sample sizes required to detect beneficial effect of a treatment agent are extremely large for subjects treated near the end of the therapeutic window, when the magnitude of benefit is small.

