2.3.3 Primary Safety Objective

The primary safety objective is to test the hypothesis that treatment with TSC is not associated with increased occurrence of serious adverse events in hyperacute stroke subjects. The study endpoint analysis to evaluate this hypothesis will be comparison of the frequency of SAEs in the TSC and placebo groups.

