2.7 Randomization

This protocol is using the step-forward, pre-encounter method of randomization that has been developed for rapid availability of research study agents in emergency trials. Each ambulance will be carrying only one study kit at any time, the next kit in its permuted random block sequence. Randomization will be 1:1 between active TSC and placebo. When that ambulance enrolls a subject, the subject will be assigned to the treatment group of the study agent kit the ambulance is carrying at the time. Subjects will be considered enrolled in the trial upon study drug injection.

A Schedule of Events is included as an Appendix 8.1 to this protocol.

The study design is shown in Table 4.

Table 4. Study Design

On Ambulance Within 2 hours of first stroke symptoms

- Perform mLAPSS
- Determine study eligibility in consultation with PHAST-TSC central enrolling physician
- Explicit informed consent or EFIC enrollment
- Perform GCS; Los Angeles Motor Scale (LAMS); Paramedic Global Impression of Change Score (PGIC)
- Obtain heart rate; blood pressure; body weight estimate
- Administer study drug (TSC or placebo) as IV injection

Emergency Department Arrival

- Informed Consent, if enrolled by EFIC
- SOC demographics; heart rate; blood pressure; body weight; pregnancy screening; labs (hematology, chemistry, coagulation); troponin
- SOC brain imaging done within 48 hours of Emergency Department arrival
- Performs mRS; BI; NIHSS
- tPA dose
- Concomitant medications/therapies
- Adverse events

24 Hours

- Obtain Informed Consent if enrolled by EFIC and not obtained at previous visit
- SOC heart rate; blood pressure; labs (hematology, chemistry, coagulation); troponin
- SOC body weight; pregnancy screening if not obtained during previous visit
- Concomitant medications/therapies
- Adverse events
- Performs NIHSS

48 Hours

- Obtain Informed Consent if enrolled by EFIC and not obtained at previous visit
- SOC heart rate; blood pressure; labs (hematology, chemistry, coagulation); troponin
- Concomitant medications/therapies
- Adverse events
- Performs NIHSS

Day 4 (If discharged prior, by phone)

- Obtain Informed Consent if enrolled by EFIC and not obtained at previous visit
- SOC heart rate; blood pressure; labs (hematology, chemistry, coagulation); troponin
- Concomitant medications/therapies
- Adverse events
- Performs mRS; BI; NIHSS

Day of Discharge

- Concomitant medications/therapies
- Adverse events
- Discharge date and destination

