3.1.6 Adverse Event Reporting Requirements

Each subject will be evaluated for the development of AEs. It is the responsibility of the investigator to document all AEs occurring during this investigation, whether or not the AE is considered drug-related. All AEs will be reported to the Sponsor via the CRF. Non-serious AEs will be reported from study drug administration through hospital discharge. SAEs will be reported from study drug administration through study completion (Day 90 visit or early termination). SAEs require expedited review and will be reported by the site to the Sponsor or designee by telephone or electronically within 24 hours of discovery. The nature of each event, date and time of onset, outcome, frequency, intensity, action taken with respect to dosage, whether it was serious or non-serious, and relationship to treatment should be documented. Signs and symptoms should be grouped into a single diagnosis and reported as a single AE when appropriate. SAEs should be followed by the investigator to resolution, or, if the SAE is not expected to resolve, it should be followed until stabilization.

AEs should be documented in terms of a medical diagnosis(es) when possible. AEs not previously documented at Baseline as pre-existing conditions will be recorded in the CRF.

The following definitions will be utilized when classifying AEs:

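### After a single ambulance bolus, Protocol 2.8.1 allows follow-up to end for reasons other than consent and 3.1.6 then closes SAE reporting, so Day-90 mRS and new SAEs may go uncollected

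*Protocol*

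**What the plan says.** Protocol section 2.2 describes one bolus given by paramedics and adds: "No additional study drug will be administered in the hospital". Section 2.7 fixes the moment of entry: "Subjects will be considered enrolled in the trial upon study drug injection".

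Section 2.8.1 opens its list with "The following events are considered sufficient reason to discontinue a subject from the study". The list holds the subject's own withdrawal, non-compliance, an AE ("The subject experienced an AE that in the investigator's opinion precludes continued participation"), a protocol violation ("The subject incurred a significant protocol violation that constitutes a safety hazard or significantly confounds the interpretation of the data from that subject"), the sponsor's request, and termination of the study. It does not separate withdrawal of consent from the other reasons. Nor does it say that outcome or safety data are still collected after discontinuation.

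Section 3.1.6 sets the SAE window: "SAEs will be reported from study drug administration through study completion (Day 90 visit or early termination").

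The Synopsis gives the primary efficacy endpoint as "Global disability level on the utility-weighted modified Rankin Score (UW-mRS) Assessment at 90 days in all subjects". Section 2.3.3 gives the primary safety analysis as "comparison of the frequency of SAEs in the TSC and placebo groups". Under section 2.8.3, dosed subjects are not replaced.

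**The concern.** In a multi-dose trial a list like that in 2.8.1 can be read as grounds for stopping study drug while observation continues. Here no drug remains to be stopped once the subject is enrolled, so each listed event is a ground for ceasing to observe a randomized, dosed subject.

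Four of the reasons have nothing to do with consent. Two are plausibly tied to outcome: the AE, and the violation judged to confound the subject's data. The second is in effect an analysis decision taken after randomization and used to stop data collection. For non-compliance and the sponsor's request the link to outcome is unknown.

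Both primary comparisons are exposed. A missing Day-90 mRS weakens an endpoint defined in all subjects. A subject discontinued because of an AE also leaves the window in which new SAEs or death would be reported. An analysis plan can model missing scores but cannot recover outcomes that were never collected, so the matter belongs in the protocol.

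**Working it through.** **1. What discontinuation can mean.** Sections 2.2 and 2.7 together leave no study treatment after enrolment. The phrase in 2.8.1 concerns leaving the study, so it can only mean the end of follow-up.

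**2. Whether another shown rule fills the gap.**
- Section 2.8.2 requires contact attempts for a subject who fails to return. It seeks the reason and safety information, not the mRS, and does not address subjects discontinued under 2.8.1.
- Section 3.1.6 requires SAEs to be followed to resolution or stabilization. That does not extend the reporting of new ones.
- Under 3.1.6, non-serious AEs are reported only to hospital discharge, so they give no cover afterwards.

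**3. SAE window left open.** The uncovered share of calendar time is (90 − t)/90 for early termination on day t.
- t = 4: 86/90 = 96%.
- t = 30: 60/90 = 67%.

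This measures time, not expected SAEs; the text shown gives no SAE timing.

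**4. Illustration for the primary endpoint.** There is no protocol figure to reproduce: the text shown states no SD, effect size, alpha, power or withdrawal rate.

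*From the protocol:* 160 subjects at 1:1, hence 80 per arm.

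*Assumed:* mean utility 0.60 in both arms (no true effect), SD 0.35, lost subjects' mean utility u = 0.20, complete-case comparison, two-sided 5% level.

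*Formulas,* with w subjects lost from an arm (wT in TSC, wP in placebo):
- Observed arm mean = (48 − u·w)/(80 − w), where 48 = 80 × 0.60.
- Bias = TSC mean − placebo mean.
- SE = SD·√[1/(80 − wT) + 1/(80 − wP)].
- Error = P(|Z + bias/SE| > 1.96).

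*Worked case, 4 lost on TSC and 0 on placebo:* TSC mean = (48 − 0.8)/76 = 0.6211; bias = 0.0211; SE = 0.35·√(1/76 + 1/80) = 0.0561; bias/SE = 0.38; error = 6.6%.

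| Lost (TSC, placebo) | Bias | Bias/SE | Error | SD 0.40 / 0.30 | u = 0.40 / 0 |
|---|---|---|---|---|---|
| 1, 0 | 0.0051 | 0.09 | 5.1% | | |
| 2, 1 | 0.0052 | 0.09 | 5.1% | | |
| 2, 0 | 0.0103 | 0.18 | 5.4% | | |
| 4, 0 | 0.0211 | 0.38 | 6.6% | 6.2 / 7.2% | 5.4 / 8.7% |
| 8, 4 | 0.0234 | 0.41 | 6.9% | 6.5 / 7.6% | 5.5 / 9.4% |
| 8, 0 | 0.0444 | 0.78 | 12.2% | 10.5 / 14.9% | 6.8 / 21.6% |
| 4, 4 or 8, 8 | 0 | 0 | 5.0% | 5.0 / 5.0% | 5.0 / 5.0% |

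Losing poor-outcome subjects mainly from TSC flatters TSC; the reverse pattern flatters placebo.

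**5. Power.** Assuming 80% power with complete data, 80 per arm detects (1.96 + 0.84)·√(2/80) = 0.443 SD. Losing 5% or 10% of Day-90 scores lowers power to 78.0% or 75.7%. Lost power is thus the lesser issue; outcome-related loss is the main one.

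**The case against.** - **The SAE link rests on an undefined term.** In the text shown, early termination is not defined, and 2.8.1 uses terminated only of the study. A study-level reading would leave SAE reporting intact for discontinued subjects. That is possible but less natural, because in both 2.5 and 3.1.6 the term stands beside the subject's Day 90 visit. The efficacy half does not depend on it.
- **Much of the protocol is not shown.** Sections 2.9 to 2.14.8, 3.1.4 and 3.1.5, the text after 3.1.6.2 and the Schedule of Events could contain a retained-follow-up rule. This stands as a limit. Such a rule would still need reconciling with 2.8.1 and 3.1.6, and an early-termination visit alone would yield neither a Day-90 mRS nor later SAEs.
- **Earlier mRS scores exist.** Section 2.7 schedules the mRS at ED arrival, Day 4 and Day 30, so an analysis could draw on them and do better than complete cases. That is fair and makes the illustration pessimistic. An earlier score is still not the Day-90 outcome.
- **Exposure may be small and similar by arm.** The list is permissive, it deletes no collected data, SAEs already reported are followed up, and section 2.2 blinds everyone except those who prepare and inject the drug. Withdrawal would then differ by arm mainly if AEs do. Losing one or two subjects moves the error only to 5.1–5.4%, and 8 versus 0 is an extreme case. All of this stands, but whether serious AEs differ by arm is what the primary safety objective is meant to test.

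**Conclusion.** The point holds and should be fixed. As shown, the protocol allows follow-up of a dosed subject to end for four reasons unrelated to consent, against a Day-90 endpoint in all subjects and an SAE comparison by arm. On the natural reading of early termination, new SAEs and deaths after that date also go unreported.

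The size cannot be determined from the document. On the assumed values above, error runs from 5.0% with equal loss, through 6.6% (4 versus 0) and 6.9% (8 versus 4), to 12.2% (8 versus 0). Across the SDs and lost-subject utilities tried, the last case spans 6.8% to 21.6%. These figures show how the bias scales with unequal, outcome-related loss and do not predict what will happen. The conclusion itself rests on the wording and is subject to the sections not shown.

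**What to change.** In 2.8.1, limit the end of follow-up to two cases: (a) consent to continue is withdrawn or refused by the subject or representative, including for subjects enrolled under EFIC; and (b) the study is terminated. Record the other listed events as deviations or AEs, and keep the subject in follow-up for the Day-90 mRS, vital status and SAEs.

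In 3.1.6, state that SAEs are collected to Day 90 for every dosed subject except in cases (a) and (b). That also removes the ambiguity in early termination.

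The cost is protocol wording in two sections and a few more Day-30 and Day-90 contacts, which the visit schedule in 2.7 already contains. The change concerns data collection only.

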2.8.2 Subjects Lost to Follow-up

The investigator will attempt to contact any subject that fails to return in order to evaluate the reason the subject has not returned and to obtain follow-up safety information. All attempts to contact the subject should be documented, including the use of registered mail with return receipt.

2.8.3 Replacement of Subjects

Subjects who have received TSC or placebo will not be replaced.

2.14.9 CT/MRI

Image scans of all CTs/MRIs obtained within 48 hours of ED arrival will be obtained for independent neuroradiologist review.

3 ADVERSE EVENT REPORTING

3.1 Definitions

3.1.1 Adverse Events

An AE is any untoward medical occurrence associated with the use of the drug in humans, whether or not considered drug related. An AE is any unfavorable and unintended sign (e.g., an abnormal laboratory finding), symptom, or disease temporally associated with the use of a drug, without any judgment about causality. This includes changes in anatomical, physiological, or metabolic functions as indicated by physical examination signs, symptoms, and/or laboratory changes or medical occurrence which develops or worsens while enrolled in this study regardless of whether the event is considered related to the investigational drug. Enrolled is defined as a subject that is assigned to treatment and is dosed with TSC or placebo.

A suspected adverse reaction means any AE for which there is a reasonable possibility that the drug caused the AE. For the purposes of Investigational New Drug (IND) safety reporting, "reasonable possibility" means there is evidence to suggest a causal relationship between the drug and the AE. The Sponsor or designee will evaluate the available evidence and make a judgment about the likelihood that the drug actually caused the AE.

Events occurring before the first TSC dose are to be considered pre-existing conditions and should be recorded as medical history. Unless a worsening occurs, they should not be considered AEs.

Abnormal laboratory values or test results constitute AEs only if they are considered clinically significant and are associated with clinical signs or symptoms or require therapy. Clinically significant abnormal laboratory values will be documented in the subject's case report form (CRF). Neurologic worsening, defined as $a \ge 4$ point worsening on the NIH Stroke Scale, will be captured as an AE or SAE per the medical opinion of the investigator.

Events **not** considered to be AEs are:

• Hospitalization for treatment which was elective or pre-planned for a pre-existing condition that did not worsen

Events not considered to be SAEs are:

• Treatment on an emergency outpatient basis for an event not fulfilling any of the definitions of serious and not resulting in hospital admission.

• Hospital admissions less than 24 hours in duration.

3.1.2 Serious Adverse Events

Serious adverse events (SAEs) are AEs that pose a threat to the subject's life or functioning based on the following outcome/actions regardless of whether the event is considered related to the investigational drug:

- Results in death
- Is life-threatening
- Requires in-patient hospitalization or prolongation of existing hospitalization
- Results in persistent or significant disability/incapacity
- Is a congenital anomaly/birth defect
- Other events, based on medical judgment, which jeopardize the subject and require medical/surgical intervention to prevent one of the outcomes above.

3.1.3 Unexpected

Any adverse event where the nature, specificity or frequency of the event is not consistent with either: 1) the known or foreseeable risk associated with the procedures involved in the research that are described in the protocol or Investigator Brochure; or 2) the expected natural progression of any underlying disease, disorder, or condition of the subject(s) experiencing the adverse event and the subject's predisposing risk factor profile for the adverse event.

Refer to Appendices, Section 8.3 for the PHAST-TSC List of Expected Adverse Events.

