3.1.6.1 Severity

- Mild: Awareness of signs or symptoms, but easily tolerated and are of minor irritant type causing no loss of time from normal activities. Symptoms do not require therapy or a medical evaluation; signs and symptoms are transient.
- Moderate: Events introduce a low level of inconvenience or concern to the participant and may interfere with daily activities but are usually improved by simple therapeutic measures; moderate experiences may cause some interference with functioning.
- Severe: Events interrupt the participant's normal daily activities and generally require systemic drug therapy or other treatment; they are usually incapacitating.

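### The definition of an unexpected event in section 3.1.3 leaves out severity, so a more severe or fatal form of a foreseeable event type is classed as expected

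*Protocol*

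**What the plan says.** Section 3.1.3 of the protocol calls an event unexpected on these terms: "Any adverse event where the nature, specificity or frequency of the event is not consistent with either" of two references. The first is "the known or foreseeable risk associated with the procedures involved in the research that are described in the protocol or Investigator Brochure". The second is "the expected natural progression of any underlying disease, disorder, or condition of the subject(s) experiencing the adverse event", joined to a further condition, "and the subject's predisposing risk factor profile for the adverse event". The section then sends the reader to a list: "Refer to Appendices, Section 8.3 for the PHAST-TSC List of Expected Adverse Events".

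Severity is handled elsewhere. Section 3.1.6 asks the investigator to document "The nature of each event, date and time of onset, outcome, frequency, intensity, action taken with respect to dosage", among other items. Section 3.1.6.1 defines three grades, the highest being events that "generally require systemic drug therapy or other treatment; they are usually incapacitating". Neither section connects the grade to expectedness.

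On reporting, section 3.1.6 states that "SAEs require expedited review and will be reported by the site to the Sponsor or designee", within 24 hours of discovery.

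**The concern.** Expectedness is a judgement made case by case. A single case can differ from the reference in its kind or in how severe it is; whether it is too frequent can be seen only across cases. The definition tests kind (nature and specificity) and frequency, but not severity. A reader who applies it literally to an event type that the protocol or Investigator Brochure describes as mild, and that turns out life-threatening or fatal, has no ground for calling it unexpected.

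This matters here because section 2.2 has the study drug given in the field to subjects with acute stroke, and the synopsis covers both ischemic and hemorrhagic stroke. Drug harm in such subjects could plausibly appear as a familiar kind of event in a worse form. At stake is the label given to such a case and whatever individual reporting depends on that label.

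**Working it through.** The point rests on the wording of a definition. The protocol gives no figure to reproduce, and no arithmetic applies. The check sets the sections side by side.

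1. **What can make an event unexpected (3.1.3).** Three attributes: nature, specificity, frequency. Severity is not named.

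2. **Whether nature already covers severity (3.1.6).** It does not on the protocol's own usage. Section 3.1.6 lists nature, outcome, frequency and intensity as separate items to document, and 3.1.6.1 gives severity its own scale. A word that stands beside intensity in one section cannot be assumed to contain it in another.

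3. **How the two references combine (3.1.3).** Because an event must be inconsistent with either reference to be unexpected, fitting one of them is enough to make it expected.

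4. **Applying the rule to single cases of a foreseeable type:**

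| Case | Nature | Specificity | Frequency | Class under 3.1.3 |
|---|---|---|---|---|
| Occurs at the severity described | consistent | consistent | cannot be judged | expected |
| Occurs at a greater severity | consistent | consistent | cannot be judged | expected |
| Is fatal, though not described as such | consistent | consistent | cannot be judged | expected |

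The three rows get the same class. The feature that separates them is not an input to the rule.

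5. **What depends on the class.** In the sections at hand, these do not use expectedness:
   - the definition of an SAE, which includes death and life-threatening events (3.1.2);
   - the 24-hour report of SAEs to the sponsor and their expedited review (3.1.6);
   - the capture of a worsening of 4 or more NIHSS points as an AE or SAE (3.1.1);
   - the sponsor's judgement of causality (3.1.1);
   - the comparison of SAE frequency by arm (2.3.3) and the objectives on organ-specific SAE classes and mortality (2.3.4).

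   What remains is the expectedness classification itself and any expedited reporting that relies on it. Sections 3.1.4 and 3.1.5 and Appendix 8.3, where such a rule or severity limits on listed events might stand, are not in the text at hand. That is not a fault of the plan.

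**The case against.** The strongest reply is that only a label is at issue. Every fatal or life-threatening event is an SAE, reaches the sponsor within 24 hours and is counted in the comparison by arm, whatever its class. No section at hand uses the word unexpected to start or withhold an action, and Appendix 8.3 may state severity levels. This stands as a limit on reach: the point is about how a case is classed after receipt, not about whether it is captured. It does not remove the defect, because 3.1.3 states a rule and that rule puts cases of clearly different severity in one class.

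A second reply is that frequency is one of the attributes and would catch an excess. That holds for accumulated data but not for one case.

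A third is that naming severity may change little, since a severe or fatal complication can itself fit the natural course of stroke. This stands in part. With severity added, a case becomes unexpected only if it is more severe than both references would lead one to expect.

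A reader might also infer that the second reference exempts anything in keeping with the course of stroke, so that any bleed, decline or death after the bolus is expected. The text does not support that. The event must also fit the subject's own risk factor profile, and it remains subject to the tests of nature, specificity and frequency. An event atypical for that subject, or of an unusual specific type, still fails. There is therefore no need to replace the second reference for suspected reactions.

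**Conclusion.** The point holds in a limited form. Section 3.1.3 omits severity, and by its own terms it classes a more severe or fatal form of a foreseeable event type as expected. In a single case nothing in the definition flags the difference.

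The effect is confined to the expectedness classification and any expedited reporting built on it. It does not touch SAE capture, the 24-hour report or the between-arm safety comparison.

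Its size cannot be put in numbers. A reader might multiply an assumed SAE rate by the roughly 80 subjects expected on TSC (160 randomized 1:1, so 160 / 2 = 80). The protocol sections at hand give no such rate, the product would count subjects and not events, and it would take in every stroke complication. Only those more severe than described are affected.

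The conclusion assumes that neither Appendix 8.3 nor sections 3.1.4 and 3.1.5 already tie expectedness to severity. If they do, the gap is narrower, but the definition in 3.1.3 should still agree with them.

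**What to change.** In section 3.1.3, name four attributes: nature, severity, specificity or frequency. Say that a fatal outcome counts under severity, because the scale in 3.1.6.1 stops at severe and has no fatal grade. Add one sentence stating that an entry in the Appendix 8.3 list is expected only at the severity described in the protocol or Investigator Brochure. Check sections 3.1.4 and 3.1.5 for consistency with the revised definition.

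The cost is one word and a sentence or two, with no change to endpoints, sample size or treatment. The downside is that a few more cases will be classed as unexpected and reviewed individually.
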